### 5.2.1. Overall Response Rate (ORR)

#### Definition

Overall response rate (ORR) is defined as the proportion of subjects who achieve partial response (PR) or better according to the RECIST version 1.1, including the subjects with either confirmed best overall response of CR or PR during the study (and prior to subsequent therapy if any).

#### Estimand

The primary estimand, the main clinical quantity of interest to be estimated in the study, is defined by the following 4 components:

Population: Participants with AR expressing locally advanced or recurrent/metastatic SGC.

Variable: Overall response.

Intercurrent event: Subsequent therapy, Response after the start of subsequent therapy will not be considered.

Population level summary: Overall response rate (ORR)

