CYCLE DAY		Day 1	Day 8 (±1 day)	Day 15 (±1 day)	Day 1	Day 15	Day 1	Day 1	Day 1	Within 30 days after last dose	Every 6 months (±14-day)	Unless otherwise specified, study visits/procedures have a ±2-day time window
												progression are observed.
Brain MRI or CT	X	As clinically indicated										Required at screening only. Brain MRI or CT will not be mandatory during the course of the study intervention unless signs of brain metastases are observed.
FDG-PET	X	As clinically indicated										Required at screening only. If bone lesions are suspected, must have confirmation of bone metastasis by CT or MRI. FDG-PET will not be mandatory during the course of the study intervention unless signs of disease

Phase	Screening	Treatment									Follow-up ^e	Notes
		Cycle 1			Cycle 2		Cycle 3	Cycles 4-6	Cycle 7 until EOT	EOT		
CYCLE (defined as 28 days)	Within 28 days before C1D1, unless otherwise specified	Cycle 1			Cycle 2		Cycle 3	Cycles 4-6	Cycle 7 until EOT	EOT	Follow-up	
CYCLE DAY		Day 1	Day 8 (±1 day)	Day 15 (±1 day)	Day 1	Day 15	Day 1	Day 1	Day 1	Within 30 days after last dose	Every 6 months (±14-day)	Unless otherwise specified, study visits/procedures have a ±2-day time window
												progression are observed.
Survival status and subsequent anticancer therapy											X	
Safety Evaluations												
Physical examination	X	X	X	X	X	X	X	X	X	X	X	Refer to Section 8.2.1. At screening, the general appearance of the participant, height, weight, and examination of the skin, ears, nose, throat, lungs, heart, abdomen, extremities, musculoskeletal system, lymphatic system, and nervous system at minimum. After screening, weight will be obtained,

Phase	Screening	Treatment									Follow-up ^e	Notes	
		Cycle 1			Cycle 2		Cycle 3	Cycles 4-6	Cycle 7 until EOT	EOT			
CYCLE (defined as 28 days)	Within 28 days before C1D1, unless otherwise specified												
CYCLE DAY		Day 1	Day 8 (±1 day)	Day 15 (±1 day)	Day 1	Day 15	Day 1	Day 1	Day 1	Day 1	Within 30 days after last dose	Every 6 months (±14-day)	Unless otherwise specified, study visits/procedures have a ±2-day time window
													and limited symptom-directed physical examinations will be conducted.
Vital signs	X	X	X	X	X	X	X	X	X	X	X		Blood pressure, heart rate, and body temperature at screening; afterwards only blood pressure will be measured.
12-lead ECG	X	As clinically indicated											
ECOG PS	X	X	X	X	X	X	X	X	X	X	X		
Clinical Laboratory Tests^d													
Hematology	X	X	X	X	X	X	X	X	X	X	X		

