6.5.1. Permitted Medications

Examples of permitted medications are listed below:

- Symptomatic treatment: Supportive care, such as antibiotics, analgesics, transfusions, and diet, and concomitant medications for the symptomatic treatment of related toxicities (Grades 1 to 4) may be administered according to the standard of care at the site, and the treating physician's discretion, as clinically indicated.
- Chronic supportive therapies: Ongoing supportive therapies are permitted.
- Palliative radiotherapy: Radiotherapy for symptomatic control is permitted, but should not include any radiation to target lesions.
- Surgical intervention may be permitted if disease could be resected radically due to the effect of the study intervention but must be approved by the sponsor's medical monitor on an individual basis prior to implementation.

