6.7. Intervention During the Follow-up Phase

During the follow-up phase, telephone contact may be made to determine the survival status and subsequent anticancer therapy, unless the participant has died, is lost to follow-up, or has withdrawn consent. If the information on the survival status and subsequent anticancer therapy is obtained via telephone contact, written documentation of the communication must be available for review in the source documents. If the participant has died, the date and cause of death will be collected and documented on the eCRF.

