9.4.2.2. Secondary Endpoints

Treated population will be used for analyses of secondary endpoints unless otherwise specified.

Clinical benefit rate (CBR) is defined as the proportion of participants who achieve a confirmed best overall response of CR, PR, or stable disease for at least 24 weeks based on RECIST version 1.1. The CBR and its 95% exact Clopper-Pearson CI will be calculated for the response-evaluable population.

Disease control rate (DCR) is defined as the proportion of participants who achieve a confirmed best overall response of CR, PR, or stable disease based on RECIST version 1.1. The DCR and its 95% exact Clopper-Pearson CI will be calculated for the response-evaluable population.

Progression-free survival (PFS) is defined as the time from the date of the initial dose of study intervention to the date of first documented disease progression as defined in the RECIST version 1.1, or death due to any cause, whichever occurs first. For participants who have not progressed and are alive, data will be censored at the last disease evaluation before the start of any subsequent antitumor therapy.

Overall survival (OS) is defined as the time from the date of the initial dose of study intervention to the date of the participant's death. If the participant is alive or the vital status is unknown, then the participant's data will be censored at the date the participant was last known to be alive.

Time to response (TTR) is defined among responders (with a CR or PR) as the time between date of the initial dose of study intervention and the first efficacy evaluation that the participant has met all criteria for CR or PR.

Duration of response (DOR) will be calculated among responders from the date of initial documentation of a response (CR or PR) to the date of first documented evidence of progressive disease as defined in RECIST version 1.1. For participants who have not progressed, data will be censored at the last disease evaluation before the start of any subsequent antitumor therapy.

Progression-free survival and OS will be summarized using Kaplan-Meier estimates for the treated analysis population. Duration of response will be summarized using Kaplan-Meier estimates for the responders. Time to response (TTR) will be summarized among responders by calculating descriptive statistics.

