### **3.1. Selection rule of response evaluable participants who are used in IA and FA**

In the primary analysis of interim and final analysis, 12 and 24 response evaluable participants (response evaluable population) who has been evaluated at least 24 weeks from the initiation of study intervention or whose disease evaluation of primary endpoint has been determined within 24 weeks after the initiation of study intervention are analyzed respectively. ie, The 12 and 24 response evaluable participants who meet the at least one condition listed below will be analyzed in the primary analysis of IA and FA respectively.

1. Who evaluated at least 24 weeks from the initiation of study intervention (has cycle 7 visit efficacy disease assessment).
2. Whose ICRR disease evaluation is confirmed as  $\geq$ PR within 24 weeks from the initiation of study intervention (disease evaluation of primary endpoint is determined at the first confirmed date of  $\geq$ PR)
3. Whose ICRR disease evaluation is PD within 24 weeks from the initiation of study intervention (disease evaluation of primary endpoint is determined at the first PD date of ICRR)
4. Who completed study participation (disease evaluation of primary endpoint is determined at death date, the date of withdrawal from consent, the last contact date if the participant is lost of follow up)
5. Who started subsequent therapy (disease evaluation of primary endpoint is determined at the date of subsequent therapy initiation)

If there are more than 12 or 24 response evaluable participants who meet the condition above at the timing of IA or FA, response evaluable participants are selected in order of the date of obtaining informed consent, the date of first study intervention and study site number from the participants who meet the condition above.

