#### **4.7. Subsequent Anticancer Therapies**

Subsequent therapies received after discontinuation of study treatment will be summarized.

The following imputation rule will be used for missing start dates for subsequent therapies:

- a. If all parts of the start date are missing, the date will be imputed with the date after the discontinuation date.
- b. In the case where only the start day of therapy is missing, it will be replaced by the day after the discontinuation date if the therapy starts in the same month and year as the discontinuation date. Otherwise, it will be replaced by the first of the month.
- c. If both the start day and month of therapy are missing, the start day and month will be replaced by the day and month of the date after the discontinuation date if the therapy and the discontinuation occur in the same year; otherwise, it will be replaced by 1st of January.

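### Does the ORR analysis need a separate rule for tumour resection that the protocol permits during the study?

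*SAP*

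**What the plan says.** Protocol 6.5.1 lists surgery among the permitted therapies: "Surgical intervention may be permitted if disease could be resected radically due to the effect of the study intervention". Each case needs the medical monitor's prior approval. The radiotherapy item just before it excludes target lesions; the surgery item has no such limit.

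The SAP limits response by time in three places:
- The ORR definition (5.2.1) counts a "confirmed best overall response of CR or PR during the study (and prior to subsequent therapy if any".
- The estimand (5.2.1) has one entry: "Intercurrent event: Subsequent therapy, Response after the start of subsequent therapy will not be considered".
- Condition 5 of the selection rule (3.1) reads: "Who started subsequent therapy (disease evaluation of primary endpoint is determined at the date of subsequent therapy initiation".

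The CBR and DCR definitions (5.3.1, 5.3.2) use the same limit. The PFS and DOR censoring tables (Tables 4 and 6) refer to subsequent anticancer therapy.

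The term is not defined. SAP 4.7 says: "Subsequent therapies received after discontinuation of study treatment will be summarized". In the Schedule of Activities the row "Survival status and subsequent anticancer therapy" is marked only for follow-up, and Protocol 6.7 adds: "During the follow-up phase, telephone contact may be made to determine the survival status and subsequent anticancer therapy". For participants without progression, Protocol 9.4.2.2 uses broader wording: "data will be censored at the last disease evaluation before the start of any subsequent antitumor therapy".

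**The concern.** If subsequent therapy means only treatment given after study drug has stopped, resection during treatment does not end the response window, and later scans still count. Appendix 9 defines complete response of target lesions by their disappearance. Taken literally, the surgeon could bring that about. A participant with stable disease, or with a partial response not yet confirmed, might then become a confirmed responder partly through surgery.

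The primary endpoint is meant to measure drug effect. With 24 participants and a final threshold of 8 responders, one classification can decide the trial. An estimand would normally be expected to cover an event that the protocol itself allows.

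**Working it through.** **Inputs.** Null ORR 14% and alternative 40% (Protocol 9.2, SAP 1.4). Looks at 12 and 24 response-evaluable participants; futility at 1 or fewer of 12; efficacy at 7 or more of 12, or 8 or more of 24 (Protocol Table 3, SAP Table 1). Stated Type-1 error 1.3% and power 80.5% (Protocol 9.5). Confirmation at 4 weeks or later (SAP 5). The documents give no frequency of resection.

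**Step 1: reproduce the design.** Let X1 and X2 be independent Bin(12, p). Then

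P(reject) = P(X1 ≥ 7) + Σ(x = 2 to 6) P(X1 = x) · P(X2 ≥ 8 − x).

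- p = 0.14: 0.0004 + 0.0129 = 0.0133 (stated 1.3%).
- p = 0.40: 0.1582 + 0.6472 = 0.8054 (stated 80.5%).

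Both agree.

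**Step 2: compare the readings.**
- *Resection ends the window.* Protocol 9.4.2.2 speaks of any subsequent antitumor therapy, in rules that govern endpoints (PFS and DOR). Radical resection of a tumour fits that description.
- *Resection does not end the window.* SAP 4.7 describes a summary of later treatments and how to impute their start dates. The Schedule of Activities and Protocol 6.7 say when information is collected. None of these sets the endpoint cut-off.

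The first reading is the natural one for an analyst deriving ORR.

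**Step 3: what must happen for harm.** All of these are needed:
1. The participant becomes radically resectable through drug effect, although entry requires T4b, N2c/N3, equivalent unresectable recurrence or distant metastasis (Protocol 5.1).
2. Surgery takes place with stable disease or an unconfirmed response; a response confirmed earlier counts on either reading.
3. The analyst takes the narrow reading.
4. Central review scores the removed lesion as a response. Appendix 9 (4.4.2) usually makes a timepoint not evaluable when only some lesions are measured. The Imaging Manual, not among the documents, may have its own rule.

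**Step 4: effect of one such response.** At the final look:

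| Responders | P(X ≥ x), n = 24, p = 0.14 | Clopper-Pearson 95% lower limit |
|---|---|---|
| 7/24 | 0.0415 | 12.6% |
| 8/24 | 0.0134 | 15.6% |

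*Case among the second 12.* The decision flips only if X1 is 2 to 6 and the genuine total is 7:

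Σ(x = 2 to 6) P(X1 = x) · P(X2 = 7 − x) = 0.0925 at p = 0.40 and 0.0271 at p = 0.14.

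*Case among the first 12.* There are three routes: X1 of 2 to 5 with total 7; X1 = 1 (futility avoided) with X2 ≥ 6; X1 = 6 (interim efficacy reached) with X2 ≤ 1.
- p = 0.40: 0.0894 + 0.0058 + 0.0035 = 0.0987.
- p = 0.14: 0.0262 + 0.0010 + 0.0014 = 0.0286.

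**Step 5: allow for rarity.** Assume that 1% to 10% of trials contain such a case, independently of the genuine count.
- ORR 40%: 0.0925 × 0.01 = 0.09% up to 0.0987 × 0.10 = 0.99%.
- ORR 14%: 0.0271 × 0.01 = 0.03% up to 0.0286 × 0.10 = 0.29%.

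*Futility stop.* It is avoided when X1 = 1, with probability 0.0174 at 40% and 0.3197 at 14%. Multiplied by 1% to 10%, this gives 0.02% to 0.17% and 0.3% to 3.2%. Avoiding the stop is not success: X1 = 1 followed by X2 ≥ 6 has probability 0.10% at 14% before the multiplier.

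**The case for a change.** The strongest case is about pre-specification, not frequency. The trial is open-label and single-arm, and the sponsor declares efficacy or futility. Without a written rule, a choice might be made after a participant's outcome is known. Surgery depends on tumour shrinkage, so an unconfirmed partial response at surgery is plausible. The text requiring discontinuation for non-protocol anticancer treatment (Protocol 7.1) does not settle the matter, because this surgery is allowed by the protocol. The excised-lesion text in Protocol 8.1 concerns baseline only. A heavier assumption also gives a larger effect: if surgery raised the counted null response rate by two points, from 14% to 16%, the rejection probability would rise from 1.33% to 2.82%, above 2.5%.

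Part of this stands. The term is undefined, and no text links it to resection. The two-point scenario, however, means 24 × 0.02 = 0.48 surgery-made responses per trial on average. That is a great many for an event needing every step above, and resectability through drug effect should be rarer when the drug does little. Sponsor discretion is limited because the decision rests solely on centrally reviewed response and fixed boundaries. An operated participant could also be traced: other therapies, including non-pharmacologic ones, are recorded until 30 days after the last dose (Protocol 6.5), and individual tumour response is listed (SAP 5.2.1).

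Nor is there one obviously right rule. Cutting every endpoint at surgery would make an operated participant with an unconfirmed response a non-responder, although the protocol allows surgery only when the drug made it possible. Other estimand strategies are defensible.

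**Conclusion.** The concern identifies missing detail, not an error. The ordinary meaning of subsequent antitumor therapy covers radical resection, and an analyst applying it would stop counting at surgery. No rule in either document is shown to give a wrong result, and the boundaries, Type-1 error and power stand.

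Under the assumed 1% to 10% frequency, the efficacy decision would change in 0.09% to 0.99% of trials at an ORR of 40% and 0.03% to 0.29% at 14%. These figures are generous, because the frequency refers to cases in which the narrow reading and a favourable central read have already occurred. They rest on a frequency that the documents do not supply, on at most one such case per trial, and on its independence from the genuine count. The contents of the Imaging Manual are unknown. No change to the plan follows.

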#### Analysis Methods

An ORR will be tested using exact test based on the binomial distribution, and the null hypothesis for ORR of 14% will be rejected and efficacy will be declared if statistical significance is observed using boundary based on the O' Brien-Fleming alpha spending function. In addition, exact Clopper-Pearson 95% CI of ORR will be calculated based on the binomial distribution. Waterfall plot will be provided for maximal percentage reduction of sum of target lesion diameters from baseline. Swim lane plot and spider plot whose horizontal axis is time from the date of initial dose of study agent, and another swim lane plot whose horizontal axis is actual time will be provided.

Individual tumor response will be listed.

### **5.3. Secondary Endpoints**

The analyses of (CBR, DCR, TTR, DOR) will be conducted based on the data of the response evaluable participants who are evaluated at least 24 weeks after the initiation of study intervention or confirmed disease evaluation before 24 weeks observation. The same analysis based on all available data of response evaluable population is conducted as supplemental analysis.

The analyses of (OS, PFS) will be conducted based on treated population using all available data of treated population. Sensitivity analyses will also be performed using the response evaluable population.

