## 2.2. Analysis Set

For purposes of analysis, the following populations are defined:

Population	Description
Enrolled	All participants who sign the ICF.
Treated	All participants who receive at least 1 dose of study intervention. This population will be used for all analyses including efficacy, safety, and biomarker unless otherwise specified.
Response evaluable	All participants who are AR positive by local test and who are confirmed evaluable by an independent central radiology review (ICRR). Also, all participants who receive at least 1 dose of study intervention and who have at least 1 postbaseline disease assessment or died due to disease progression before the first postbaseline disease assessment. This population will be considered for primary efficacy analysis.  Note: Confirmed evaluable by an independent central radiology review means the participant had at least one target lesion confirmed by ICRR.
Pharmacokinetic	All participants with at least 1 apalutamide and/or N-desmethyl apalutamide concentration data after the first study intervention administration.

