#### **5.3.3. Progression-free survival (PFS)**

##### **Definition**

Progression-free survival (PFS) is defined as the time from the date of the initial dose of study intervention to the date of first documented disease progression as defined in the RECIST version 1.1, or death due to any cause, whichever occurs first.

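### The OS and PFS sensitivity analysis uses a set whose membership depends on events after first dose, so it drops early non-progression deaths and cannot cleanly test the treated-population result

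*SAP*

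**What the plan says.** SAP 5.3 sets the main analysis: "The analyses of (OS, PFS) will be conducted based on treated population using all available data of treated population". It then adds: "Sensitivity analyses will also be performed using the response evaluable population". Protocol 9.4.2.2 also plans both endpoints in the treated population and does not mention this second analysis.

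The two sets differ in kind. SAP 2.2 defines the treated population by dosing alone: "All participants who receive at least 1 dose of study intervention". The response evaluable population needs local AR positivity and evaluability by independent central radiology review (ICRR), which a note explains: "Confirmed evaluable by an independent central radiology review means the participant had at least one target lesion confirmed by ICRR". A second sentence, opening "Also, all participants who receive at least 1 dose of study intervention", limits it to those "who have at least 1 postbaseline disease assessment or died due to disease progression before the first postbaseline disease assessment".

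Both endpoints start at first dose. OS ends at death, whatever the cause. PFS ends at progression "or death due to any cause, whichever occurs first". The first scheduled postbaseline scan is at Cycle 3 (Protocol 1.3).

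**The concern.** Time zero is the first dose, but membership of the sensitivity set is settled weeks later, partly by the outcome being measured. Anyone who enters through a scan has survived to that scan. Two participants who die on the same day before any scan are handled in opposite ways: a death attributed to progression stays in, and any other death is removed. Cause of death is recorded on the eCRF (Protocol 6.7), and neither document describes adjudication. The study is open-label and single-arm, so an all-cause endpoint should not depend on that attribution.

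At stake is what the sensitivity result means. It would be read as evidence that the treated-population curves are robust. With about 24 participants, one or two removals can move a curve visibly.

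**Working it through.** **Plan's own figure.** The documents give no OS or PFS assumption and no expected number of non-evaluable participants, so there is nothing on this point to reproduce. The stated Type-1 error and power (1.3% and 80.5%, Protocol 9.5) concern ORR and do not enter here.

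**Timing.** Cycles last 28 days, so Cycle 3 Day 1 is Day 1 + 2 × 28 = Day 57. Imaging may be done up to 7 days earlier.

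**Who leaves the set, on the cumulative reading.**
- (a) Treated participants who die of a non-progression cause before any scan.
- (b) Treated participants with no ICRR-confirmed target lesion, whatever their outcome.
- (c) Living participants with no postbaseline scan. They stay in OS follow-up, because stopping treatment is not withdrawal from the study (Protocol 7.1).

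**Group (a) alone.** Let q be the fraction of treated participants in group (a), with nobody else excluded. After the first scan, S_treated(t) = (1 − q) × S_set(t), so S_set(t) = S_treated(t) / (1 − q). With q assumed and a true 6-month OS rate of 80%:
- q = 1/25: 0.80 / 0.960 = 83.3%
- q = 2/26: 0.80 / 0.923 = 86.7%
- q = 3/27: 0.80 / 0.889 = 90.0%
- q = 0: 80%, no effect

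On the median scale, assume an exponential curve with a 24-month median in the sensitivity set. Solving (1 − q) × exp(−λt) = 0.5 with λ = ln 2 / 24 gives treated-population medians of about 22.6, 21.2 and 19.9 months for the three values of q.

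**All groups together.** Take an assumed core of 22 participants who stay in the set: 11 deaths at months 4, 6, …, 24, and 11 censored from month 28. Core Kaplan-Meier OS at 6, 12 and 24 months is 20/22, 17/22 and 11/22, or 90.9%, 77.3% and 50.0%. Then add back those the definition removes:

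| Removed from the treated set | Treated OS at 6/12/24 months | Shift on removal (points) |
|---|---|---|
| 2 non-progression deaths at month 1 | 83.3 / 70.8 / 45.8% | +7.6 / +6.4 / +4.2 |
| 2 from group (b) or (c), alive at month 30 | 91.7 / 79.2 / 54.2% | −0.8 / −1.9 / −4.2 |
| 1 such early death and 2 alive at month 30 | 88.0 / 76.0 / 52.0% | +2.9 / +1.3 / −2.0 |

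The 24-month shift runs from −4.2 to +4.2 points, and in the third row the curves cross.

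**PFS.** A death with no postbaseline scan fits two rows of SAP Table 4: the death row (event at date of death) and the row for no postbaseline assessment (censored at first dosing date). No precedence is given. If the death is an event, as the definition in SAP 5.3.3 implies, removing it raises the curve. If it is censored at first dose, removing it changes nothing. Living participants with no scan are censored at first dose, so removing two of them from the assumed data moves the curve by 0.0 points.

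**The case against.** A reader might infer that the sensitivity curves can only move up. The documents do not support that: groups (b) and (c) are also removed, and removing people who outlive others' deaths lowers a Kaplan-Meier curve. The offset has limits. Measurable disease is an entry criterion (Protocol 5.1), so group (b) needs central review to disagree with the site, and removing group (c) does not move PFS.

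A reader might also infer that early toxic deaths would be hidden. They would not be. The main OS analysis uses all treated participants. SAP 6.4 summarises deaths by period and primary cause, and Table 7 plans a table and a listing of adverse events leading to death, on the treated population.

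The word 'Also' in SAP 2.2 could open an alternative route into the set. Then a locally AR-positive participant with an ICRR target lesion would stay in without a scan, and early non-progression deaths would largely be kept. The cumulative reading is more natural, but the text does not settle it.

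Finally, neither endpoint is tested, and efficacy and futility rest on ORR alone. That stands, and it caps the importance of the point.

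**Conclusion.** The point holds in a limited form. On the cumulative reading of SAP 2.2, the sensitivity set is conditioned on post-dose events and on attributed cause of death. Dropping early non-progression deaths by itself biases OS upward, and PFS too if those deaths are events. Combined with the other exclusions, the net direction is undetermined. Agreement or disagreement with the treated-population result would therefore be hard to interpret.

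The size depends wholly on an unknown count. One to three such deaths, with no other exclusions, would show an 80% rate as 83.3% to 90.0%; none would leave it unchanged. The consequence is confined to the sensitivity result, so this is a cheap improvement of low importance.

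**What to change.** In SAP 5.3, define the OS and PFS sensitivity set by baseline facts only: treated, AR-positive by local test, and at least one ICRR-confirmed baseline target lesion, with no condition on a postbaseline scan or cause of death. In Table 4, state that a death without a postbaseline scan is a PFS event, consistent with SAP 5.3.3.

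A landmark analysis at week 8 is not a good substitute. It would also drop the early progression deaths that the current set keeps, and for PFS it would need a progression-free condition as well.

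The cost is one sentence in SAP 5.3 and one line in Table 4. The data are already collected, and the protocol text on OS and PFS need not change. The downside is that the sensitivity estimate may be slightly less favourable and its population will no longer match the ORR population exactly.
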